10.3 Clinical Events Committee Review

At regular intervals, an independent Clinical Events Committee (CEC) will review all adverse events and deaths.

The CEC will consist of a minimum of three (3) non-sponsor employed physicians (including one vascular neurologist and one electrophysiologist), and the CEC chairperson. The CEC members will not include participating VICTORY AF investigators. The purpose of the CEC is to conduct a medical review of events for subjects participating in the study. At least three CEC members must adjudicate, at a minimum, all deaths, all neurologic events, and all AEs related to any component of the system. All other AEs will be adjudicated by at least one physician member of the CEC.

Sponsor personnel may facilitate and participate in CEC meetings but will be non-voting members. The sponsor will provide the CEC with the investigator's description and classification of each AE in addition to sponsor's assignment of the MedDRA key term. Additionally, the sponsor's assignment of the complication or observation classification will be provided for all system and procedure related AEs. The CEC is responsible for reviewing the investigator's assessment and classification of each event. The CEC will review adverse events and provide a final adjudication of relatedness and seriousness as applicable for all events as well as the complication/observation classification for system or procedure related events. In addition, the CEC will determine the cardiovascular and neurological relatedness of each AE. If the CEC disagrees with the investigator's classification of the event, the rationale will be provided to the investigator. If the investigator agrees with the CEC, this will be documented accordingly. If the investigator does not agree with the CEC classification, both determinations will be documented within the study report. However, the CEC determination will be used for analysis purposes.

Additionally, the CEC will determine whether each AE meets the definition of a procedure and/or device related stroke in Table 5 or the TIA definition in Table 10.

10.4 Steering Committee (SC)

The steering committee will be an advisory body to the VICTORY AF study team and be responsible for collaboration and guidance on study goals, design, study center communications, training materials and other activities based on expertise or as agreed upon.

The study's steering committee (SC) will be comprised of non-Medtronic physicians including at least one EP and one neurologist.

10.5 Data Monitoring Committee (DMC)

Ongoing oversight for this study will be provided by an independent DMC. The DMC will consist of a minimum of at least one electrophysiologist, one neurologist, and one statistician who are not sponsor employees. The DMC will not include participating VICTORY AF investigators, members of the Steering Committee or Clinical Events Committee.

The DMC is retained to aid the sponsor in safeguarding the interests of trial participants and monitoring the overall conduct of the study. The DMC will meet at regular intervals or as

agreed upon to review accumulating study data and will be advisory to the sponsor and may provide recommendations for early termination of the trial. Review and consensus by the entire committee is required to recommend that the study should be stopped. The DMC may also make recommendations related to the selection, management and retention of subjects, improvement of adherence to protocol-specified regimens, and procedures for data management and quality control.

10.6 Market Released Event Reporting

The following definitions apply to all market released products used in the clinical study and must be reported according to standard market release reporting guidelines per geography.

Medical Device Reporting (MDR) Requirements for User Facilities (U.S.)

General Reminder for Investigators:

Per FDA regulations, Device User Facilities are required to report Medical Device Reports (MDR) on market approved products (21 CFR 803, subpart C) A Device User Facility is defined as a hospital, an ambulatory surgical facility, a nursing home, an outpatient treatment facility, or an outpatient diagnostic facility which is not a physician's office.

Vigilance Reporting (EEA)

It is the responsibility of the investigator to report all product complaints and misuse and abuse immediately via the regular channels for CE marked products. The reporting of product complaints abuse, and misuse of these CE-labeled devices is not part of the clinical study and should be done in addition to the AE reporting requirements.

10.7 Investigator Adverse Event and Device Deficiency Recording and Reporting Requirements

AEs and device deficiencies will be recorded and reported according to local regulatory requirements. Refer to Table 13 AE requirements. It is the responsibility of the Investigator to abide by the adverse event reporting requirements stipulated by the centers' IRB/MEC.

Table 13: Adverse Event and Device Deficiency Reporting Requirements

Serious Adverse Events (SAEs)	
Investigator submit to:	
Medtronic	Europe: Immediately after the investigator first learns of the event or new information in relation with an already reported event. (ISO 14155 and local law) All other geographies: Submit in a timely manner after the investigator first learns of the event.
Ethics Board	Europe: Submit to Ethics Board per local reporting requirement All other geographies: Submit per local EC requirement.
Sponsor submit to:	
Regulatory authorities	Europe: Submit to Competent Authority per local reporting requirement.
Ethics Board	Europe: Submit to Ethics Board per local reporting requirement.
Serious Adverse Device Effects (SADEs)	
Investigator submit to:	
Medtronic	Canada: Investigators are required, per the TPD Investigator Agreement, to report any incident that is related to a failure of the device or deterioration in its effectiveness, or any inadequacy in its labeling or directions for use leading to death or serious deterioration in a subject's health within 72 hours after the occurrence. (Canada Medical Device Regulations, SOR/98-282; 77, 59) Europe: Immediately after the investigator first learns of the event. (ISO 14155 and local law) All other geographies: Submit in a timely manner after the investigator first learns of the event.
Ethics Board	Europe: Inform Ethics Board about any SADE (ISO 14155) Reporting timeframe as per local MEC requirement. All other geographies: Submit per local Ethics Board requirement.
Health Canada	Canada: Investigators are required, per the TPD Investigator Agreement, to report any incident that is related to a failure of the device or deterioration in its effectiveness, or any inadequacy in its labeling or directions for use leading to death or serious deterioration in a subject's health within 72 hours after the occurrence. (Canada Medical Device Regulations, SOR/98-282; 77, 59)
Sponsor submit to:	
Regulatory authorities	Canada: Preliminary and final reporting to the Canadian Ministry of Health of events occurring inside (always) or outside Canada (in case of corrective actions) that is related to a failure of the device or a deterioration in its effectiveness, or any inadequacy in its labeling or its directions for use and has led to the death or a serious deterioration in the state of health of a patient, user or other person or could do so were it to recur. Report a) within 10 days after awareness, if incident has led to death or a serious deterioration in the state of health of a patient, user or other person b) within 30 days, if incident has not led to led to death or a serious deterioration in the state of health of a patient, user or other person, but could do so were it to recur c) as soon as possible, if incident occurred outside of Canada and is related to a corrective action. (Canada Medical Device Regulations, SOR/98-282; Mandatory Problem Reporting 59(1) , 59(2), 60 (1)) Europe: Reporting timelines as per local competent authority.

Ethics Board	Canada and Europe: Submit per local requirement (ISO 14155)
Unanticipated Adverse Device Effects (UADEs) and Unanticipated Serious Adverse Device Effects (USADEs)	
Investigator submit to:	
Medtronic	
Canada: Investigators are required, per the Therapeutic Products Directorate Investigator Agreement, to report any incident that is related to a failure of the device or deterioration in its effectiveness, or any inadequacy in its labeling or directions for use leading to death or serious deterioration in a subject's health within 72 hours after the occurrence. (Canada Medical Device Regulations, SOR/98-282; 77, 59)
 
Europe: Immediately after the investigator first learns of the effect. (ISO 14155 and local law)
 
US: Submit as soon as possible, but no later than within 10 working days after the investigator first receives notice of the effect. (21 CFR 812.150(a)(1))
 
All other geographies: Submit in a timely manner after the investigator first learns of the effect.

Ethics Board	
US: Submit as soon as possible, but no later than within 10 working days after the investigator first receives notice of the effect. (21 CFR 812.150(a)(1))
 
All other geographies: Reporting timeframe as per local Ethics Board requirement.

Health Canada	
Canada: Investigators are required, per the TPD Investigator Agreement, to report any incident that is related to a failure of the device or deterioration in its effectiveness, or any inadequacy in its labeling or directions for use leading to death or serious deterioration in a subject's health within 72 hours after the occurrence. (Canada Medical Device Regulations, SOR/98-282; 77, 59)

Sponsor submit to:	
Investigator	All geographies: Notification as soon as possible, but not later than 10 working days after the sponsor first learns of the effect. (21 CFR 812.150(b)(1))
Regulatory authorities	
Canada: Preliminary and final reporting to the Canadian Ministry of Health of events occurring inside (always) or outside Canada (in case of corrective actions) that is related to a failure of the device or a deterioration in its effectiveness, or any inadequacy in its labeling or its directions for use and has led to the death or a serious deterioration in the state of health of a patient, user or other person or could do so were it to recur. Report a) within 10 days after awareness, if incident has led to death or a serious deterioration in the state of health of a patient, user or other person b) within 30 days, if incident has not led to death or a serious deterioration in the state of health of a patient, user or other person, but could do so were it to recur c) as soon as possible, if incident occurred outside of Canada and is related to a corrective action. (Canada Medical Device Regulations, SOR/98-282; Mandatory Problem Reporting 59(1), 59(2), 60 (1))
 
Europe: All UADEs are classified as SADEs and should follow the applicable reporting requirements. (ISO 14155) and Note for Guidance on Clinical Safety Data Management: Definitions and Standards for Expedited Reporting (CPMP/ICH/377/95 3.A.1) Reporting timeframe as per local competent authority. (ISO 14155:2011 3.42)
 
US: Notification as soon as possible to FDA, but not later than 10 working days after the sponsor first receives notice of the effect. (21 CFR 812.150(b)(1))

Ethics Board	All geographies: Notification as soon as possible, but not later than 10 working days after the sponsor first learns of the effect. (21 CFR 812.150(b)(1))
All other reportable Adverse Events (system, procedure and cardiovascular-related)	
Investigator submit to:	
Medtronic	All geographies: Submit in a timely manner after the investigator first learns of the event.
Regulatory authorities	All geographies: Submit or report as required per local reporting requirement.

Ethics Board	All geographies: Submit per local Ethics Board requirement.
Device Deficiencies with SADE potential	
Investigator submit to:	
Medtronic	Europe: Immediately after the investigator first learns of the deficiency or of new information in relation with an already reported deficiency. All other geographies: Submit or report as required per local reporting requirements.
Ethics Board	Submit per local EC requirement.
Regulatory authorities	Report immediately after the investigator first learns of the event if required according to local law.
Sponsor submit to:	
Regulatory authorities	All geographies: Submit or report as required per local reporting requirements.
Ethics Board	All geographies: Submit per local Ethics Board requirement.
All other Device Deficiencies	
Investigator submit to:	
Medtronic	All geographies: Submit in a timely manner after the investigator first learns of the deficiency.
Regulatory Authorities	All geographies: Submit or report as required per local reporting requirement.
EC	All geographies: Submit per local EC requirement.

11. RISK ANALYSIS

The residual risks associated with the Phased RF System have been found to be acceptable and have been mitigated to the fullest extent possible. The potential benefits related to the use of the Phased RF System have been determined to outweigh any potential risks.

For geographies where the study devices are market-approved, there are no known incremental risks to the study subject as a result of participating in the study. These risks are documented in the product labeling. However, there are potential risks and side effects associated with an ablation and required study follow-up procedures (e.g. CT and/or MRI scans for [REDACTED] PV stenosis [REDACTED]). These risks are provided in the Informed Consent Form.

Table 14 describes the potential risks that have been identified since the TTOP-AF study and the mitigations that have been put in place to minimize the risks.

Table 14: Potential Risks and Risk Minimization

Potential Risks	Risk Minimization
Peri-procedural stroke	
Based on literature review (provided Executive Summary and Report of Prior Investigations), the continuance of oral anticoagulation prior, during and post ablation procedure reduces the risks of stroke without increasing the risk of bleeding complications, particularly with therapeutic INR (2.0-3.5).
 
Maintaining procedural ACT >350 has also been associated with reduced stroke incidence.
 
Rigorous sheath management during catheter introduction and exchanges has demonstrated a reduced likelihood of air egress during the ablation procedure.

Potential Risks	Risk Minimization

[REDACTED]
	
[REDACTED]

Pulmonary vein stenosis
	
Physician operators will be trained on visualization techniques (e.g. fluoroscopy imaging in LAO and RAO views depending on pulmonary vein target) to verify the PVAC or PVAC GOLD catheter is not situated within the tubular portion of the PV prior to ablation.

11.1 Risk-to-Benefit Analysis

The cohort of subjects for inclusion in this study is symptomatic as a result of their persistent atrial fibrillation and the failure of class I or III antiarrhythmic drug therapy. Phased RF ablation therapy offers the opportunity to reduce the episodes of atrial fibrillation and therefore reduce symptoms. Catheter ablation therapy in subjects with paroxysmal atrial fibrillation have shown improvements in symptoms and reduced episodes of atrial fibrillation.

In the United States there are no approved ablation catheters approved to treat subjects with persistent atrial fibrillation. If successful, the VICTORY AF study could demonstrate meaningful therapeutic benefit in this underserved population.

In Europe, Phased RF ablation catheters are approved to treat subjects with persistent atrial fibrillation. If successful, the VICTORY AF study could confirm meaningful therapeutic benefit in this underserved population.

12. STATISTICAL METHODS AND DATA ANALYSIS

Medtronic employees or their designated representatives will perform all statistical analysis.

Additionally, a separate Statistical Analysis Plan (SAP) will be developed to further describe statistical methods, pre-specified data handling rules, and pre-specified analyses that will be included in study reports (e.g. PMA report, final study report).

Additional exploratory analyses of the data may be conducted as deemed appropriate.

The study will be considered successful if the primary objective is met. Specifically, for the study to be successful, the observed procedure and/or device related stroke rate must be less than 1.8% and its associated exact one-sided upper 95% confidence interval must be less than 3.5%.

12.1 General Summaries

12.1.1 Description of Baseline Variables

Standard baseline and relevant medical history will be collected on the CRFs for all enrolled subjects. Baseline variables to be summarized include, but are not limited to: age, sex, race, physical exam findings, arrhythmia history, arrhythmic symptoms, baseline ECG interpretation, AF medication history, baseline MMSE score, baseline CHADS₂ score and CHA₂DS₂-VASc.

For continuous variables, mean standard deviation, median, and range will be reported. For categorical variables, frequency and percentage will be reported. Summaries of baseline information and relevant medical history will be summarized for all enrolled subjects, all subjects with a Phased RF ablation procedure (e.g. at least one Phased RF catheter placed in the left atrium), subjects randomized to the PVS assessment cohort [REDACTED]

12.1.2 Summary of Ablation Procedures

A summary of Phased RF ablation procedure information including procedure times, ablation locations, Phased RF ablation catheters used, and ablation energy modes will be summarized for procedures where at least one Phased RF ablation catheter was placed in the left atrium.

12.1.3 PVAC and PVAC GOLD catheter use

If Phased RF ablation procedures are performed with more than one PVAC model, subgroup analyses will be performed on the primary and secondary

objectives [REDACTED] by PVAC model. Specifically, should the need for a subgroup analysis occur, three subgroups will be defined as subjects ablated with only the PVAC catheter (index and reablation procedure), subjects ablated with only the PVAC GOLD catheter (index and reablation procedure), and subjects ablated with both the PVAC and PVAC GOLD catheter (e.g. index procedure with PVAC catheter and reablation procedure with PVAC GOLD catheter). For each of these objectives, Fisher's Exact test would then be used to assess the heterogeneity of the results by PVAC catheter subgroup should the need for a subgroup analysis arise.

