1.2 Phased RF System Description

The Medtronic Phased RF System is intended to be used for mapping intracardiac electrograms and to deliver precise, temperature controlled radio frequency (RF) ablation therapy within the left atrium of the heart for the treatment of atrial fibrillation. The Phased RF System includes the GENius Multi Channel Radio Frequency Ablation Generator and three anatomically designed, multi-electrode catheters:

- Pulmonary Vein Ablation Catheter (PVAC) or Pulmonary Vein Ablation Catheter GOLD (PVAC GOLD)
- Multi-Array Septal Catheter (MASC)
- Multi-Array Ablation Catheter (MAAC)

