7.15 Permissible Retreatment Ablation Procedure

All study subjects may have one reablation procedure with the Phased RF System within 180 days of their index ablation procedure under this protocol if the following criteria are met:

- Subject has not completed the 6-month follow-up visit
- Recurrent AF/AFL that cannot be controlled with antiarrhythmic drugs and/or cardioversion
- The subject has not had any other ablation procedure in the left atrium since first Phased RF ablation
- Subjects undergoing a retreatment procedure are willing to be followed for 6-months following their retreatment procedure, or until official study closure defined as when Medtronic and/or regulatory requirements have been satisfied per the Clinical Investigational Plan, whichever occurs first. Medtronic will provide a new set of target visit dates following notification of a retreatment procedure as described in section 7.6.

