Subjects will only be included in this analysis for the 6-month effectiveness objective if they have both a baseline and 6-month 48-hour ambulatory ECG monitor that are readable by the core lab or are missing a 48-hour ambulatory ECG monitor data and 6-month effectiveness failures based on other criteria at the time of the visit cutoff date. However, should the issue of missing data arise; all ablated subjects that complete the 6-month visit at the time of the visit cutoff regardless of ambulatory ECG monitor data status will be included in a tipping point analysis to evaluate the impact of missing data. Specifically, subjects completing the 6-month study visit but missing the ambulatory ECG monitor assessment who are not 6-month effectiveness failures based on other criteria will be included as successes and then iteratively included as failures in the tipping point analysis.

12.3.2 *Secondary Objective #2: Acute procedural success*

12.3.2.1 **Objective**

Confirm acute post-procedural effectiveness.

12.3.2.2 **Hypothesis**

There is no pre-specified hypothesis associated with this secondary objective.

12.3.2.3 **Definition acute procedural success**

Acute procedural success is defined as meeting all four of the following conditions:

1. Only Phased RF catheters used in the left atrium to achieve procedure success AND
2. All accessible pulmonary veins were isolated (entrance block)
3. CFAEs and high frequency intracardiac electrogram amplitudes were mapped and ablated as necessary with Phased RF System

4. Sinus rhythm is restored at the end of the ablation procedure (with or without cardioversion)

12.3.2.4 **Analysis Methods**

All ablation procedure parameters will be captured on the case report forms. For estimating the acute success rate, all subjects with an attempted ablation where at least one of the Phased RF catheters were deployed into the left atrium will be included in the denominator. The numerator will include all subjects in the denominator who met all the conditions for acute procedural success defined above. A two-sided lower 95% exact confidence interval for the acute procedural success rate will be calculated. Subjects that have a reablation attempt will be considered acutely successful if they meet all the conditions for their index procedure and conditions 1 and 4 of the acute success definition for their reablation attempt since the source of recurrent AF will be unknown.

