#### **3.1.3.3 PVAC and PVAC GOLD catheter use**

If Phased RF ablation procedures are performed with more than one PVAC model, subgroup analyses may be performed on the primary and secondary objectives as well [REDACTED] by PVAC model. Specifically, should the need for a subgroup analysis occur, three subgroups will be defined as subjects ablated with only the PVAC catheter (index and reablation procedure), subjects ablated with only the PVAC GOLD catheter (index and reablation procedure), and subjects ablated with both

the PVAC and PVAC GOLD catheter (e.g. index procedure with PVAC catheter and reablation procedure with PVAC GOLD catheter). For each of these objectives, Fisher's Exact test would then be used to assess the heterogeneity of the results by PVAC catheter subgroup should the need for a subgroup analysis arise.

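### The three-group PVAC/PVAC GOLD heterogeneity test confounds catheter model with reablation, because membership of the third group comes essentially from having a second procedure

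*Protocol*

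**What the plan says.** Protocol 12.1.3 and SAP 3.1.3.3 define three subject-level subgroups: PVAC only, PVAC GOLD only, and "subjects ablated with both the PVAC and PVAC GOLD catheter". The one example given for the third is an index procedure with PVAC followed by a reablation with PVAC GOLD. The single-model groups contain one-procedure subjects and reablated subjects who kept their model. For each objective Fisher's "Exact test would then be used to assess the heterogeneity of the results by PVAC catheter subgroup". No significance level, adjustment or stratification by number of procedures is given in the readable text.

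The protocol makes this analysis mandatory if both models are used. SAP 3.1.3.3 says only that "subgroup analyses may be performed on the primary and secondary objectives", while SAP 3.2.7, 3.3.1.7 and 3.3.2.6 make it mandatory. (SAP 3.3.2.6 sits under acute success but names 6-month effectiveness.)

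These provisions bear on the comparison:
- Protocol 1.2 lists PVAC and PVAC GOLD as alternatives.
- Protocol 7.15: "All study subjects may have one reablation procedure with the Phased RF System within 180 days" of the index procedure, on condition of recurrent AF/AFL not controlled by drugs or cardioversion.
- Protocol 12.2.3 and 12.2.5 count stroke per subject, with a 30-day window after each procedure.
- Protocol 12.3.2.4 requires a reablated subject to meet every acute-success condition at index and "conditions 1 and 4 of the acute success definition for their reablation attempt".
- Protocol 12.3.1.4 requires acute success at both procedures for 6-month effectiveness.
- Protocol 7.12 and 12.3.3.4 take the PVS scan at the first 3-month visit and do not repeat it after a later reablation.

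**The concern.** Reablation is a post-treatment outcome. A subject reaches the third group essentially by having recurrent AF/AFL and a second procedure, and each subject who switches model leaves a single-model group. The groups then differ in more than the catheter:
- **Stroke:** two risk windows instead of one.
- **Acute success:** two procedures must succeed instead of one.
- **6-month effectiveness:** the group is selected on early recurrence and also carries the two-procedure acute requirement.
- **PVS:** a scan taken before a later reablation with the other model is filed under the third group, although it reflects the index catheter only. This is misclassification rather than an effect of procedure count.

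This is the only test the readable plan names for differences between catheter models. A false signal would invite a catheter explanation for what reablation produced, and a real catheter difference would be hard to separate from reablation.

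**Working it through.** **The plan's own figures.** None is stated for this test. The primary power figures do reproduce: with 300 subjects, success means at most 5 strokes (5/300 = 1.67%, exact upper limit 3.47%; 6/300 = 2.0%, upper limit 3.91%). P(X ≤ 5) is 91.7%, 80.2% and 54.5% at true rates of 1%, 1.3% and 1.8% (stated: 90, 80, 55%), and 4.76% at 3.5%.

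**Inputs from the documents.** 30% reablated (Protocol 12.2.6). Ablated subjects: 420 × (1 − 0.26) = 310.8, taken as 311.

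**Assumptions, not in the documents.** 30–50% start on PVAC; 50–100% of their reablations use GOLD; GOLD starters stay on GOLD; no catheter effect; nominal level 0.05. Acute success is 90% at index and 90%, 97% or 99% at reablation. Stroke risk is 1% per procedure.

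**Group composition.** The third group has between 311 × 0.30 × 0.30 × 0.50 = 14 and 311 × 0.50 × 0.30 × 1.00 = 47 subjects, all reablated. In the PVAC-only group the reablated share is 0.15/0.85 = 17.6% at 50% switching and 0% at 100%. In the GOLD-only group it is 30%.

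**Expected rates with identical catheters.**
- Stroke, one procedure: 1.0%. Two procedures: 1 − 0.99² = 1.99%. Overall: 0.7 × 1.0 + 0.3 × 1.99 = 1.3%, the protocol's planning rate; 311 × 0.013 is about 4 strokes.
- Acute success, one procedure: 90%. Two procedures: 0.9 × 0.9 = 81%, 0.9 × 0.97 = 87.3%, or 0.9 × 0.99 = 89.1%.

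**Simulated rejection rates** (exact three-group Fisher test against two-group Fisher test by index model):

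| Endpoint | Three groups | By index model |
|---|---|---|
| Acute success, 90% index, 90% reablation | about 11–26% | about 4% |
| Acute success, 90% index, 97–99% reablation | about 5–9% | about 4% |
| Stroke, 1% per procedure | about 5–7% | 1–2% |

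In the first row the lowest value is at 30% PVAC starters with 50% switching, and the highest at 50% with 100%. A rerun with 3,000 trials per acute-success setting fell within these ranges; its standard error is at most √(0.26 × 0.74/3000) = 0.8 points.

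**A second set of assumptions.** Take 300 subjects, groups sized as if half start on each model, and 25–100% of reablated subjects switching in either direction. At an overall stroke rate of 1.3% the test rejects in 5.1–7.5% of trials, against 2.3–3.2% if all three groups had equal rates. For acute success the range is 11–93% (85–95% success at index, 80–95% at reablation). For 6-month effectiveness (200 subjects, 55% overall) it depends on how reablated subjects fare: about 5% if equally well, 6–19% if 10 points worse, 15–64% if 20 points worse and 31–96% if 30 points worse.

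**The case against.** The strongest reply is that this is a conditional, descriptive check. Study success rests on the primary objective alone (Protocol section 12), no alpha is attached, and Protocol 12.2.9 says its own stroke subgroups are unpowered. All of that stands, and it limits the consequence.

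The size also depends on inputs that the documents do not give. At reablation only two conditions apply: Phased RF catheters alone in the left atrium, and sinus rhythm restored with or without cardioversion. Reablation success could therefore be well above index success, and the inflation then largely disappears. It is also smaller, under 10% at 90%/90%, if only 10% of subjects start on PVAC. This stands too.

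Three stronger readings are tempting, and the documents do not support them:
- A reader might infer that any signal is really about number of procedures. The PVAC-only versus GOLD-only contrast can still show a catheter difference, recurrence is a second confounder, and the example is introduced by e.g., so other routes into the third group are not excluded.
- A reader might infer rejection far above 5% on every endpoint. For stroke at the planning rate it is about 5–7%, and for effectiveness there is no inflation unless reablated subjects do worse.
- A reader might infer that the test decides whether results may be pooled across models. The text speaks only of assessing heterogeneity.

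Finally, grouping by index catheter alone would count a stroke after a GOLD reablation against PVAC. That is a genuine drawback, so the fix needs a per-procedure display as well.

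**Conclusion.** The confounding is real and follows from the definitions, whatever the simulation inputs: the third group consists essentially of subjects with two procedures and recurrent AF/AFL, and no readable text adjusts for this. With identical catheters the false-signal rate for acute success is about 11–26% if index and reablation success are both 90%, and about 5–9% if reablation success is 97–99%. For stroke it is about 5–7%, against 1–2% by index catheter. Effectiveness is inflated only if reablated subjects do worse, and PVS can be misclassified. Apart from the 30% reablation rate, the starting mix, switching rate and per-procedure risks behind these figures are assumptions. The primary decision is untouched. The change is worth making because it is cheap and because a result from the present test would be hard to interpret.

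**What to change.** In Protocol 12.1.3 and SAP 3.1.3.3:
1. For subject-level endpoints, apply Fisher's test to two groups defined by the PVAC model used at the index procedure. State the rule for an index procedure in which both models are used.
2. Add per-procedure stroke and acute-success rates by the catheter used in that procedure, allowing for clustering within subject as already planned for acute success (Rao and Scott). An event after a reablation with the other model is then attributed to that model.
3. Show subjects treated with both models descriptively, without a test.
4. Change *may* to *will* in SAP 3.1.3.3, to match Protocol 12.1.3 and SAP 3.2.7, and name acute success in SAP 3.3.2.6.

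The cost is wording and one further table. The catheters used at each procedure are already recorded, so no new data are needed. The downside is mixed exposure in the index groups for subjects who switch, which item 2 addresses; with about four strokes expected, the per-procedure stroke display will be descriptive only.
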